7.8.3.7. Quality of Life Assessments

Food Allergy Quality of Life Questionnaire

The FAQLQ is a disease specific health-related quality of life (HRQoL) questionnaire of both subjects and their families.

It will be completed by study subjects 8 years old and older: FAQLQ-Child Form for age range 8 to 12 years old; FAQLQ-Teenager Form for age range 13 to 17 years old; and FAQLQ-Adult Form for age range 18 to 55 years old.

Parents will also complete a FAQLQ for subjects 4 to 12 years old (FAQLQ-Parent Form) and for subjects 13 to 17 years old (FAQLQ-Parent Form Teenagers).

These will be completed prior to the Screening DBPCFCs, Week 20, prior to the Exit DBPCFCs and at the EOT or ET visits. The same questionnaire will be completed throughout the study according to the subject’s age at Screening.

The number of items and domains varies by instrument administered. Each version contains 3 or 4 domains to assess different aspects of FA-related (HRQoL).

| Questionnaire | Domains | Number of Items |
|---------------|--|-----------------|
| FAQLQ-CF | Allergen Avoidance, Dietary Restrictions, Emotional Impact, and Risk of Accidental Exposure | 24 |
| FAQLQ-TF | Allergen Avoidance, Dietary Restrictions, Emotional Impact, and Risk of Accidental Exposure | 23 |
| FAQLQ-AF | Allergen Avoidance, Dietary Restrictions, Emotional Impact, Risk of Accidental Exposure, and Food Allergy-Related Health | 29 |
| FAQLQ-PF | Emotional Impact, Food-Related Anxiety, and Social and Dietary Limitations | 30 |

Abbreviations: AF = Adult Form; CF = Child Form; FAQLQ = Food Allergy Quality of Life Questionnaire; PF = Parent Form; TF = Teen Form.

Each question item employs a seven-point response scale rating from 0 (no impairment) to 6 (maximal impairment) for each FAQLQ questionnaire. The total FAQLQ scores and domain scores are calculated by dividing the sum score of completed items by the number of completed items. Missing data will not be imputed. If less than 80% of the items within each of the total FAQLQ and domain are complete, then the total score and/or the domain score will not be calculated and set as missing.

The total and domain scores of each questionnaire type will be summarized for pediatric subjects and all subjects by treatment group at each time point using actual value and change from baseline results.

Listing of the raw scores as recorded in the eCRF will be provided, sorted by treatment group and subject ID.

Food Allergy Quality of Life Parental Burden Questionnaire

Assessment of FAQL-PB will be performed prior to the Screening DBPCFCs, Week 20, prior to the Exit DBPCFCs, and at EOT or ET.

The FAQL-PB questionnaire is a self-administered 17-item questionnaire developed to measure the burden on parents with food-allergic children aged 0 to 17 years. The questionnaire contains 2 domains, emotional distress and limitation on life, that include 14 (questions 4 to 17) and 3 (questions 1 to 3) items, respectively. Each item uses a 7-point response option rating from not troubled (or not limited) to extremely troubled (or limited).

The domain scores for (emotional distress and limitation on life) which is a sum of the scores for each question within each domain will be calculated and summarized using descriptive statistics. The total score which is the sum of all the scores from all the 17 questions will also be summarized using descriptive statistics.

Listing of the raw FAQL-PB scores as recorded in the eCRF as well as the derived domain and total scores will be provided, sorted by treatment group and subject ID.

Treatment Satisfaction Questionnaire for Medication

Assessment of treatment satisfaction will be performed using the TSQM-9 at Week 20, prior to the Exit DBPCFCs, and at EOT or ET. It will be completed by the subject (or the parent for children < 12 years of age).

The TSQM-9 is a widely used instrument to assess treatment satisfaction with medication in studies where subject reported side effects have a potential to interfere with the objectives of the study. The instrument consists of 9 questions representing 3 domains: effectiveness, convenience and global satisfaction that together provide a measure of treatment satisfaction with medication from a subject's perspective. Each of the 3 domains contains 3 items. The Effectiveness scale

includes items 1-3, the Convenience scale includes items 4-6, and the Global Satisfaction scale includes items 7-9. Each item uses a 7-point response option listed as extremely dissatisfied (or inconvenient, difficult) to extremely satisfied (or convenient, easy). Items 7 and 8 have 5 response options that range from not at all confident (or not certain) to extremely confident (or certain). The scores for each TSQM-9 range from 0 to 100, with higher scores representing higher satisfaction on that domain. Each scale will be scored as: $100 * [(\text{sum of non-missing responses}) - \text{number of non-missing responses}] / \text{maximum possible score}$ of the sum of non-missing responses. If more than one item within the scale has a missing result then the scale score will not be calculated.

The scale scores (effectiveness, convenience, and global satisfaction) will be calculated and summarized using descriptive statistics.

Listing of the raw TSQM-9 scores as recorded in the eCRF as well as the derived scale scores will be provided, sorted by treatment group and subject ID.

Accidental Exposure Questionnaire

The occurrence of a safety event associated with accidental food ingestion will be reported as a food allergy episode, as per the protocol. Even if the subject does not have a reaction, the accidental exposure need still be reported. Any such event that meets the definition of an AE or SAE will also be reported as an adverse event. Incidence of accidental exposure will be collected throughout the study from the Baseline/Day 1 visit through the EOT visit.

The Accidental Exposure Questionnaire is a newly-developed self-administered questionnaire containing 11 items asking about known food allergen exposure, associated symptoms experienced (if any), and treatment received (if any) following accidental exposure to a food to which the subject is allergic. It will be completed by the subject (or the parent in the case of children < 12 years of age) immediately following any incident of accidental exposure to the known allergic food(s). Instances in which exposure is intentional, such as during study drug dosing-related exposure, are not considered accidental exposures and will not prompt use of this questionnaire. Subjects (or their parents) may use a mApp to complete the questionnaire to ensure a timely assessment of accidental exposure and its consequences.

The analysis of this endpoint will be performed by treatment group and by study period (Overall, Pre-Maintenance, Maintenance, Exit Food Challenge/Week 40, and EOT). For each period, the number of subjects experiencing any accidental exposure instance, the number of subjects experiencing accidental exposure instances in response to food source, the number of instances of each food source experienced per subject, the total number of food source instances, and the number of subjects experiencing any accidental exposure instances with and without symptoms.

All accidental exposure data will be listed by age group, treatment group, and subject.

Immunotherapy-Related Quality of Life Questionnaire

Assessment of IQoL will be collected prior to Screening DBPCFCs, Week 20, prior to Exit DBPCFCs, and at EOT or ET.

The IQoL is a newly developed questionnaire designed to assess aspects of HRQoL affected by living with an FA. In contrast to the FAQLQ, the IQoL aims to assess perceived impairment resulting from allergy to foods specifically treated by OIT. The IQoL assesses constructs identified by OIT-treated subjects as contributing to psychosocial burden in the context of their food allergen immunotherapy. The IQoL has versions for children aged 8 to 12 years (18 items) and teens/adults aged \geq 13 years (23 items), and a proxy version for parents of children with FA aged 4 to 17 years (23 items). The IQoL measures nervousness or worry about being exposed to OIT-treated food allergens, social limitations, and emotional impact. Due to the novelty and ongoing development of the IQoL, psychometric validation analyses will be conducted as part of this study to confirm its structure and psychometric properties. The scoring algorithm will be determined during the validation process.

| Questionnaire/Domain | Number of Items |
|----------------------|-----------------|
| IQoL -CF | 18 |
| IQoL -TF/AF | 23 |
| IQoL -PF | 23 |

Abbreviations: AF = Adult Form; CF = Child Form; IQoL = Immunotherapy-Related Quality of Life Questionnaire; PF = Parent Form; TF = Teen Form.

Each question item employs a 5-point response scale rating of either (Never, Rarely, Sometimes, Often, Always) for emotional impact question or (Not at all, A little bit, Somewhat, Quite a bit, Very much) for all others.

The process of scoring this questionnaire is provided below.

- Step 1: Assign the following scores to the responses: Not at all/ Never = 0; A little bit /Rarely = 1; Somewhat /Sometime = 2; Quite a bit/ Often =3; Very much / Always = 4
- Step 2: Check for missing Items: Scoring requires 75% completion of items for analysis

| Age Specific IQoL | Subdomain: Worry/Expectation of Adverse Outcome | Subdomain: Emotional Impact | Subdomain: Social Impact | Total IQoL Score |
|---------------------------|---|-----------------------------|--------------------------|------------------|
| Teenager/Adult And Parent | 5/7 items | 8/11 items | 4/5 items | 18/23 items |
| Child | 4/5 items | 6/8 items | 4/5 items | 14/18 items |

- Step 3: Calculate the following scores when data requirements are met
 - Total IQoL score within each of the 3 questionnaires

- Total score for each of the 3 subdomains within each of the 3 questionnaires as given below.

| Age Specific IQoL | Subdomain: Worry/Expectation of Adverse Outcome | Subdomain: Emotional Impact | Subdomain: Social Impact |
|-------------------|---|---|--------------------------------|
| Teenager/Adult | 7 items: 1,2,3,4,5,6,23 | 11 items: 7, 8, 9, 10, 12, 13, 15, 17, 18, 21, 22 | 5 items: 11, 14, 16, 19, 20 |
| Child | 5 items: 1, 2, 3, 4, 18 | 8 items: 5, 6, 8, 9, 11, 13, 14, 17 | 5 items: 7, 10, 12, 15, 16 |
| Parent | 7 items: 1, 2, 3, 4, 5, 6, 23 | 11 items: 7, 8, 9, 10, 12, 13, 15, 17, 18, 21, 22 | 5 items: 11, 14, 16, 19, 20 |

The total and subdomain scores of each questionnaire type will be summarized for pediatric subjects and all subjects by treatment group at each time point using actual value and change from baseline results.

Listing of the raw IQoL scores as recorded in the eCRF and derived scores will be provided, sorted by treatment group and subject ID.

Asthma Control Test or Childhood Asthma Control Test Questionnaire

For subjects with asthma, the asthma control test (ACT) (subjects ≥ 12 years of age) or childhood ACT (C-ACT) (children 4 to 11 years of age) will be collected prior to Screening DBPCFCs, Week 20, prior to Exit DBPCFCs, and at EOT or ET.

The ACT is a 5-item, subject-based, clinically validated assessment of asthma control, designed to measure dimensions of asthma control outlined in the current asthma management guidelines as defined by the NHLBI: asthma symptoms, utilization of rescue medications, and impact of asthma on everyday functioning. The ACT is a simple measure of assessing asthma control that is suitable for use with or without lung function testing. The ACT data entered on the eCRF will be automatically scored in real time via Medidata and Optum cloud-based platform, and provided as part of RAVE data extracts for SDTM data generation. The total score range from 5 (poorly controlled asthma) to 25 (well-controlled asthma). A total score of 19 or less indicates asthma is not adequately controlled. Missing data will not be imputed as the data are already scored accounting for missing data in the scoring algorithm used by Optum.

The C-ACT captures the frequency of asthma symptoms and their effect on daily function in children 4 to 11 years of age. It is composed of 7 items investigating one domain and consists of child completed items on a 4-point pictorial response, and parent/caregiver completed items on a 6-point Likert scale. The scoring of the C-ACT data is as follows:

- Step 1: Child responds to the first 4 questions (1 to 4). If the child needs help reading or understanding the question, the parent/caregiver may help, but should let the child select the response.
- Step 2: Parent/Caregiver complete the remaining three questions (5 to 7) on their own and without letting the child's response influence their answers. There are no right or wrong answers.
- Step 3: Parent/Caregiver write the number of each answer in the score box provided.
- Step 4: Parent/caregiver add up each score box for the total.
- Step 5: Parent/caregiver take the test to the doctor provider to discuss their child's total score.

The total C-ACT score provided by the parent/caregiver is entered on the eCRF. The total score range between 0 (poorly controlled asthma) and 27 (well-controlled asthma). A total score of 19 or less indicates asthma is not adequately controlled.

The total ACT or C-ACT scores will be summarized by treatment group at each time point using actual value and change from baseline results. A shift table of asthma control (adequate, not adequate, missing) will be summarized by treatment at each visit. The number of subjects with completed ACT/C-ACT questionnaires will be used as the denominator for all percentages.

Listing of the raw ACT and C-ACT scores as recorded in the eCRF and derived scores will be provided, sorted by treatment group and subject ID.

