8.1.2.4. Treatment Satisfaction Questionnaire for Medication

The TSQM-9 is a well-validated, self-administered, 9-item questionnaire developed to assess the satisfaction that patients had with their medical treatment (Bharmal, 2009). The validity and reliability of the TSQM has been demonstrated in different patient groups (Atkinson, 2004). The TSQM-9 contains 3 domains, effectiveness, convenience, and global satisfaction, that together provide a measure of treatment satisfaction with medication from the patient's perspective. Each of the 3 domains contains 3 items. Each item uses a 7-point response option listed as extremely dissatisfied (or inconvenient, difficult) to extremely satisfied (or convenient, easy). Items 7 and 8 have 5 response options that range from not at all confident (or not certain) to extremely confident (or certain). The scores for each TSQM-9 range from 0 to 100, with higher scores representing higher satisfaction on that domain. It will be completed by the subject (or the parent for children < 12 years of age).

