4.4. Exploratory Endpoints

The exploratory endpoints of the study are:

- Change from baseline in eliciting dose of each individual Reactive Food at the Exit DBPCFC
- Changes from baseline in biomarkers, including, but not limited to, specific immunoglobulin E (sIgE) and specific immunoglobulin G subclass 4 (sIgG4), of all foods contained in ADP101
- Change from baseline in SPT for all foods contained in ADP101
- Quality-of-life changes over time using the following:
 - Food Allergy Quality of Life Questionnaire (FAQLQ)
 - Accidental exposure questionnaire
 - Immunotherapy-related quality-of-life (IQoL) questionnaire
 - 9-Item Treatment Satisfaction Questionnaire for Medication (TSQM 9)
 - Food Allergy Quality of Life–Parental Burden (FAQL-PB) questionnaire
- Proportion of subjects who develop confirmed new FAs to previously Non-reactive Foods at Screening as demonstrated by the Exit DBPCFC
- Incidence of AEs that lead to withdrawal from the study and/or discontinuation of study drug

- Incidence and shifts of clinically significant abnormalities in laboratory tests, vital signs, and spirometry forced expiratory volume in the first second (FEV1)/peak expiratory flow rate (PEFR)
- Frequency of allergic reaction AEs during treatment normalized for duration of treatment

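### The SAP's TSQM-9 scoring formula cannot produce the 0 to 100 range the SAP states; separately, two IQoL completion minimums fall below the SAP's own 75% rule

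*SAP*

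**What the plan says.** **TSQM-9.** Protocol section 8.1.2.4 states: "The scores for each TSQM-9 range from 0 to 100, with higher scores representing higher satisfaction on that domain". SAP section 7.8.3.7 repeats that range. The SAP assigns three items to each of three scales (Effectiveness 1–3, Convenience 4–6, Global Satisfaction 7–9) and describes the responses by label: "Each item uses a 7-point response option listed as extremely dissatisfied (or inconvenient, difficult) to extremely satisfied (or convenient, easy"). Two items differ: "Items 7 and 8 have 5 response options that range from not at all confident (or not certain) to extremely confident (or certain"). No numeric codes are given for these labels.

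The formula follows directly. It multiplies 100 by the sum of answered items less the number answered, and divides by the "maximum possible score}$ of the sum of non-missing responses". The missing-item rule is: "If more than one item within the scale has a missing result then the scale score will not be calculated". One missing item per scale is therefore allowed.

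**IQoL.** The same section codes items 0 to 4 and requires 75% of items to be complete before scoring. It then tabulates the minimums:

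| Form | Worry | Emotional | Social | Total |
|---|---|---|---|---|
| Teenager/Adult and Parent | 5/7 | 8/11 | 4/5 | 18/23 |
| Child | 4/5 | 6/8 | 4/5 | 14/18 |

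**The concern.** A score that rescales a sum to 0–100 needs the same offset in numerator and denominator. Here the offset appears only in the numerator, so the formula and the range stated just before it disagree. The missing item codes add a second uncertainty. Subtracting the number answered implies coding from 1, but the same section codes another seven-point instrument from 0: "Each question item employs a seven-point response scale rating from 0 (no impairment) to 6 (maximal impairment) for each FAQLQ questionnaire".

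If the formula were programmed as written with 1-coded items, every score above the floor would be too low, and Global Satisfaction would have a different ceiling from the other two scales. With 0-coded items, negative scores would be possible. TSQM-9 is not administered at Screening or Day 1, so what gets reported is the level on the claimed 0–100 scale rather than a change from baseline.

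For IQoL, text and table disagree on whether a Teenager/Adult or Parent subdomain with exactly 5 of 7 or exactly 8 of 11 items answered is scored.

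**Working it through.** **Inputs (SAP 7.8.3.7).** There are three items per scale. Items 1–6 and 9 have 7 options; items 7 and 8 have 5. At most one item may be missing. Let k be the number answered, S their sum and M the largest possible S.

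**Formula as written:** score = 100 × (S − k) / M.

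**Can it reach 100?** The highest score is 100 × (M − k) / M. This equals 100 only if k = 0, so no complete or nearly complete scale can reach 100.

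**Coded from 1** (lowest S = k, so the floor is 0):

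| Scale | M | Ceiling as written |
|---|---|---|
| Effectiveness, Convenience, complete | 7+7+7 = 21 | (21−3)/21 = 85.7 |
| Effectiveness, Convenience, one missing | 14 | (14−2)/14 = 85.7 |
| Global, complete | 5+5+7 = 17 | (17−3)/17 = 82.4 |
| Global, item 9 missing | 10 | (10−2)/10 = 80.0 |
| Global, item 7 or 8 missing | 12 | (12−2)/12 = 83.3 |

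Scores are understated by 14.3% for Effectiveness and Convenience. For Global the understatement is 17.6% when complete, 20.0% without item 9, and 16.7% without item 7 or 8. A subject choosing the middle option throughout should score 50 but scores (12−3)/21 = 42.9, or (10−3)/17 = 41.2 on Global.

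**Coded from 0** (lowest S = 0):

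| Scale | M | Range as written |
|---|---|---|
| Effectiveness, Convenience, complete | 18 | −3/18 = −16.7 to 15/18 = 83.3 |
| Global, complete | 4+4+6 = 14 | −3/14 = −21.4 to 11/14 = 78.6 |
| Global, item 9 missing | 8 | −2/8 = −25.0 to 6/8 = 75.0 |
| Global, item 7 or 8 missing | 10 | −2/10 = −20.0 to 8/10 = 80.0 |

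The stated 0–100 range is not reproduced under either coding.

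**Does the obvious repair depend on coding?** Using M − k as denominator gives 0 to 100 for 1-coded items (18/18 and 14/14). With 0-coded items it gives −3/15 = −20.0 to 100 for Effectiveness and Convenience, and −3/11 = −27.3 to 100 for Global. The coding therefore has to be settled first.

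**IQoL.** Compare each tabulated minimum with 0.75n:

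| n | 0.75n | Table | Percent | Up / nearest / down |
|---|---|---|---|---|
| 7 | 5.25 | 5 | 71.4 | 6 / 5 / 5 |
| 11 | 8.25 | 8 | 72.7 | 9 / 8 / 8 |
| 5 (three cells) | 3.75 | 4 | 80.0 | 4 / 4 / 3 |
| 23 | 17.25 | 18 | 78.3 | 18 / 17 / 17 |
| 8 | 6.00 | 6 | 75.0 | 6 / 6 / 6 |
| 18 | 13.5 | 14 | 77.8 | 14 / 14 / 13 |

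Two of eight cells fall below 75%. Rounding up matches 6 cells, rounding to nearest 7, and rounding down 3, so no single rule explains the table.

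**The case against.** The strongest defence is that the maximum in the denominator was meant as the maximum of the bracketed quantity, that is 18 or 14. With items coded from 1 this gives exactly 0–100, and the range is stated immediately beforehand. But the denominator is described as the maximum of the sum of answered items, and the numerator uses that same sum before the subtraction. The reading repairs the text; it does not follow from it.

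The denominator phrase carries conversion residue, so the typeset page is worth a look. No missing term is visible, however, and the phrase is complete as it stands.

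It is also fair that the subtraction makes little sense unless items start at 1, and that nothing codes TSQM-9 from 0. The 0-coded results are conditional. They matter because the SAP leaves the coding open and the natural repair fails if items are stored from 0.

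On IQoL, the SAP says the algorithm will be settled during validation, and the table gives programmers usable numbers. That makes the thresholds arguably provisional. It does not remove the conflict, since the SAP goes on to give a scoring process with both the 75% rule and the table.

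The case for low impact stands. SAP section 4.4 lists these instruments under "The exploratory endpoints of the study are", and no between-arm test is specified for them. With complete 1-coded data the distortion is a constant factor within each scale (6/7, or 14/17 for Global), so arm ordering and relative differences are preserved. The factor varies only for Global with one item missing. The source data also remain visible: "Listing of the raw TSQM-9 scores as recorded in the eCRF as well as the derived scale scores will be provided".

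**Conclusion.** The concern holds, at minor severity. As written, the TSQM-9 formula contradicts the range stated in both documents. Scores top out at 85.7 and 82.4 if items are coded from 1, or span −16.7 to 83.3 and −21.4 to 78.6 if coded from 0. These figures assume the option counts in the SAP and consecutive integer codes. The IQoL mismatch is also real but narrow: it affects two cells, on the Teenager/Adult and Parent forms, and only respondents with exactly 5 of 7 or 8 of 11 items answered.

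The conclusion concerns the SAP text only. Section 11 places programming specifications in a separate document, which may already score the scale differently. Any error is recoverable from the listed raw scores, and no primary or secondary result depends on it.

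**What to change.** **TSQM-9.** Confirm from the instrument or eCRF how the items are stored, and state the codes in the SAP. Then:

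- If stored from 1, make the denominator the maximum possible sum of the answered items minus the number answered. That is 18 for Effectiveness and Convenience (12 with one item missing) and 14 for Global (8 without item 9, 10 without item 7 or 8).
- If stored from 0, remove the subtraction from the numerator and keep the maximum possible sum of the answered items as denominator. With all items answered this is again 18 and 14.

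Either route gives 0 to 100.

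**IQoL.** Reconcile text and table when the algorithm is confirmed at validation. One option is to raise the two cells to 6/7 (85.7%) and 9/11 (81.8%). The other is to state a rounding convention, align 18/23 with it and reword the 75% requirement. Under rounding to nearest, 18/23 becomes 17/23 (73.9%) and three cells would then sit below 75%. The documents do not settle which was intended.

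**Cost.** One check of stored codes, one formula, and one IQoL sentence or up to two table cells. No new data are needed.

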8.2.7.2. Asthma Control Assessment

Assessment of asthma control in asthmatic subjects using the Asthma Control Test (ACT) questionnaire (Schatz, 2006) or Childhood Asthma Control Test (C-ACT) questionnaire (Bime, 2016) will be performed as specified in the SoA.

For subjects aged 12 years and older, the ACT has 5 questions, each recorded on a scale of 1 (worst control) to 5 (complete control). The total ACT is the sum of the 5 scores, and ranges from 5 (worst control) to 25 (total control). A total score of 19 or less indicates that asthma is not adequately controlled. Missing data will not be imputed. If any of the 5 questions have a missing response, the total ACT score will not be calculated.

The C-ACT is validated for assessing asthma control in children aged 4 to 11 years (Liu, 2007). It includes 4 questions for the child and 3 questions for the parent to complete. Child responses range from 0 (worst control) to 3 (complete control). Parent responses range from 0 (every day) to 5 (no days). The sum of all 7 questions will make up the total score. The total C-ACT score for subjects under 12 years of age will range from 0 (worst control) to 27 (well controlled). A score of 19 or less indicates uncontrolled asthma. Missing data will not be imputed. If any of the questions have a missing response, the total C-ACT score will not be calculated for that subject.

A listing of the results from the questionnaire, including the total score, will be provided and sorted by treatment group, subject identification, and time point.

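### SAP 7.8.3.7 does not carry through the protocol's rule that a C-ACT with a missing item has no total, and its asthma-control shift table has a missing category that its own denominator excludes

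*SAP*

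**What the plan says.** Protocol 8.2.7.2 sets one rule for both instruments. For the ACT: "If any of the 5 questions have a missing response, the total ACT score will not be calculated". For the C-ACT: "If any of the questions have a missing response, the total C-ACT score will not be calculated for that subject". It also rules out imputation, and the only output it plans is a listing.

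SAP 7.8.3.7 describes C-ACT scoring in five steps. The child answers four questions, the parent answers three, the parent writes each score in a box, the parent adds the boxes, and the form goes to the doctor. Then "The total C-ACT score provided by the parent/caregiver is entered on the eCRF". That description contains no missing-item rule and no recalculation from the items. For the ACT, the SAP says that nothing will be imputed because the vendor's scoring algorithm has already dealt with missing data. It does not say how.

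The SAP then goes beyond a listing. It plans summaries of the total and its change from baseline, and a shift table with three categories (adequate, not adequate, missing). For percentages it states: "The number of subjects with completed ACT/C-ACT questionnaires will be used as the denominator for all percentages".

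**The concern.** A hand-added total does not show whether every box was filled. If a parent skips an item and adds the rest, the result looks like any other total, although the protocol says that no total should exist. Zero is the worst-control end of each C-ACT item, so the error can only lower the score. The SAP's shift table compares that score with a cut-off, so a skipped box can appear as a loss of asthma control. Protocol 8.2 groups asthma control with the safety assessments, in subjects who take allergen every day.

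The denominator is a second and independent problem. A table that includes missing as a category but divides by completed forms cannot sum to 100% once a form is missing.

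**Working it through.** **Inputs (Protocol 8.2.7.2).** "It includes 4 questions for the child and 3 questions for the parent to complete". Child items score 0 to 3 and parent items 0 to 5. "A score of 19 or less indicates uncontrolled asthma"; the SAP uses the same cut-off. ACT: five items, each scored 1 to 5.

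**Stated ranges reproduced.**
- C-ACT maximum = 4 × 3 + 3 × 5 = 12 + 15 = 27; minimum 0.
- ACT = 5 × 1 to 5 × 5 = 5 to 25.

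Both match the protocol and the SAP.

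**One blank added as 0 (an assumption; the documents do not say what a parent does with a blank).** Recorded total = true total − v, where v is the value the skipped item would have had. A true total of 20 or more is misclassified if true total − v ≤ 19.
- Child item, v at most 3: possible only for true totals up to 19 + 3 = 22, that is 20 to 22.
- Parent item, v at most 5: possible only for true totals up to 19 + 5 = 24, that is 20 to 24.
- Highest recorded total with one blank: 27 − 3 = 24 (child) or 27 − 5 = 22 (parent). Both are above 19, so true totals of 25 to 27 never cross. A true 27 recorded as 22 stays in the adequate category but enters the change-from-baseline summary 5 points too low.

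Within these ranges a crossing depends on v. A true 24 crosses only if the skipped parent item was worth 5; a true 20 crosses if it was worth 1 or more. Of all 2,928 response patterns with a true total of 20 or more, leaving one given child item blank moves 71.7% to 19 or less, and one given parent item 94.3%. These are counts of patterns, not probabilities for patients.

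**Two or three blanks.** The highest recorded total is:
- two child items: 27 − 6 = 21
- one of each: 27 − 8 = 19
- two parent items: 27 − 10 = 17
- three items: at most 27 − 9 = 18

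So two blanks that include a parent item, or any three blanks, always give 19 or less.

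**Shift table.** With c completed and m missing forms at a visit, the percentages sum to (c + m)/c. The counts below are assumed.
- 6 adequate, 2 not adequate, 2 missing: 6/8 + 2/8 + 2/8 = 75% + 25% + 25% = 125%.
- 17 completed, 3 missing: 20/17 = 117.6%.
- The missing row alone passes 100% only when m exceeds c: 6 missing and 4 completed give 6/4 = 150%.

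**Is the scoring change authorised elsewhere?** Protocol 9.4 lets the SAP supersede that section, and the scoring rule is in 8.2.7.2, outside it. SAP section 9, which lists changes from the protocol, names no scoring change. In the same SAP section, the FAQLQ (80% of items), the TSQM-9 (no more than one missing item per scale) and the IQoL (75% of items) each have a completeness rule. The C-ACT has none.

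**The case against.** A reader might infer that the SAP overrides the protocol's rule. The documents do not support that. The SAP is silent on missing C-ACT items, SAP 3.1 refers to Protocol section 8 for details of assessments, and the precedence clause does not reach 8.2.7.2. The protocol rule still stands; the fault is that the scoring steps do not apply it.

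A reader might also infer a conflict for the ACT. None can be shown. Both documents rule out imputation, and the vendor's algorithm may return no total for an incomplete form, as the protocol requires. The blank-as-zero argument applies only to the C-ACT.

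The C-ACT error needs a chain of events: an item is skipped, the parent adds the rest, and the site accepts the form without query. The SAP's steps assume that every item is answered. Protocol 10.1.5 requires source data verification, investigator sign-off on the eCRF and data quality checks, and these may catch some cases. The SAP lists raw and derived scores, so the items may also be held. This stands as a limit on how often the error would occur. It does not supply the missing rule, because an entered total can agree with the form's total while a box on the form is empty.

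On the denominator, the sum passes 100% only if the missing row is given a percentage, and the table shells are a separate document. The adequate and not-adequate percentages among completers are unaffected. That stands, but the SAP's wording covers all percentages, so on a plain reading the missing row is included.

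**Conclusion.** The point holds as a gap in scoring and tabulation. The SAP does not carry the protocol's no-total rule into C-ACT scoring. If a parent adds over a blank, one skipped item can move a true total of 20 to 24 (parent item) or 20 to 22 (child item) to the not-adequate category. It would be too strong to say that any form with a blank reads as uncontrolled asthma, because one blank never moves 25 to 27 and need not move a lower total. It would also be too strong to say that errors at baseline and exit cannot cancel: the same item skipped at both visits could partly cancel in the change score. For the ACT, the vendor's rule is simply unknown.

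The shift-table percentages sum to more than 100% whenever a post-baseline form is missing and that category is given a percentage.

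The importance is low. The output is descriptive and limited to subjects with asthma, and the C-ACT part to those aged 4 to 11. Asthma severity by the NHLBI criteria is analysed separately, and exacerbations are reported as adverse events. The primary analysis is not affected.

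**What to change.** - **C-ACT:** derive the total by program from the item responses. Where only a total is held, check it against the source form. Set it to missing if any item is missing, as in Protocol 8.2.7.2, and state this in SAP 7.8.3.7.
- **ACT:** confirm that the vendor's score follows the same rule, and record the answer in the SAP.
- **Shift table:** show missing as a count without a percentage, or use all subjects with asthma as the denominator.

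The cost is a source check of a small number of questionnaires, a few sentences in the SAP, and a few more totals set to missing.
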